1 **25/10/2022**

2

3 **Retraining the automatic reaction to physical activity and sedentary stimuli in adults 60 years of**  
4 **age or older: A cognitive bias modification protocol**

5

6 **ABSTRACT**

7 **Background:** To counteract the pandemic of physical inactivity, current interventions mainly rely on  
8 reflective processes that focus on increasing the motivation to be physically active. Yet, while these  
9 interventions successfully increase intention, their effect on actual behavior is weak. Recent findings  
10 suggest that this inability to turn the intention into action is explained by negative automatic reactions to  
11 stimuli associated with physical activity. These automatic reactions could be particularly strong in older  
12 adults, who are more likely to associate physical activity with fear, pain, or discomfort. **Objective:** The aim  
13 of this program is to test the effect of an intervention that targets the automatic processes underlying  
14 physical inactivity in older adults. Training older adults to inhibit the automatic attraction toward sedentary  
15 stimuli is hypothesized to increase physical activity, thereby contributing to improving physical functioning  
16 and quality of life. **Methods:** To test these hypotheses, older adults will be enrolled in a controlled double-  
17 blinded study with a 1, 3, 6, and 12-month follow-up. Participants will be randomized (1:1 ratio) to receive  
18 a 12-session cognitive-bias modification training for 3-week based on a go/no-go task in an experimental  
19 or a control condition (placebo). The primary outcome will be the number of steps per week. Secondary  
20 outcomes include automatic approach-avoidance tendencies, explicit affective attitudes toward physical  
21 activity, physical function, and quality of life. **Discussion:** The study is expected to inform public-health  
22 policies and improve interventions aiming to counteract the pandemic of physical inactivity.

23

24 **KEYWORDS:** Attentional Bias, Aging, Exercise, Sedentary Behavior

25 **Background**

26 Over the past two decades, society has encouraged people to be more physically active [1-3]. As a  
27 result, most individuals are now aware of the positive effects of regular physical activity and have the  
28 intention to exercise [4]. Yet, this intention is not sufficient, as exercise plans are often not executed [5].  

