140 of 400 trials for a total of 30 min. To assess the effect of the intervention, primary and secondary outcomes  
141 will be collected for one week, the week before the first session, the week following the last session of the  
142 intervention, as well as 1, 3, 6, and 12 months post intervention.

143

144 **Figure 3.** Protocol timeline.

145

146 ***Allocation and blinding***

147 Participants and research assistant will be blinded to the groups’ allocation. The participant blinding  
148 success will be appraised by asking them to guess in what group there were at the trial termination. Besides,  
149 the research assistant blinding success will be appraised via detecting the group allocation (Experimental  
150 vs. Control) by research assistant at the end of data collection phase. The randomization will be generated  
151 on a computer and an independent coworker will carry out the randomization. The participant’s  
152 identification number will be used to determine the sequence of randomization. Participants will be  
153 randomized in a 1:1 ratio between the intervention and active control condition.

154

155 ***Outcomes***

156 Participants will first respond to questions related to their age, sex (male, female), weight, and  
157 height.

158 ***Primary outcome***

159 The project focuses on device-based measures of physical activity and sedentary behaviors.  
160 Specifically, the primary outcomes collected using a physical-activity tracker will be the number of steps.  
161 Participants will be given the tracker and will be trained on how to wear the device (ie, over the right hip,  
162 affixed to an elastic belt, preferably worn under their waistbands). Currently, the waist based Actigraph is  
163 the most used device to objectively measure physical activity. Participants will be instructed to used it all

164 day long for 7 days and not to used it during shower or when they sleep at night. If the participant uses the  
165 tracker less than for 4 days in a row for at least 7 hours per day, they will not be included in the study. The  
166 number of steps measured in the week pre- and post-intervention, as well as 1, 3, 6, and 12 months after the  
167 intervention will be used as the primary outcome.

168 ***Secondary Outcomes***

169 The secondary outcomes will allow the examination of indirect health effects related to an increase  
170 in physical activity and a decrease in sedentary behavior.

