225 Statistical analyses will be performed according to the intention-to-treat principle and abide by the  
226 Consolidated Standards of Reporting Trials (CONSORT) guidelines. A sequential analysis will be  
227 conducted with an interim analysis after 50% of the data is collected and the other analyses after all data is  
228 collected [47]. Based on the Pocock boundary, the threshold for significant p-values will be .0294 [48]. If  
229 the effect is significant at the interim analysis, thereby indicating that the data provide support for the

230 hypothesis, data collection will be terminated. Mean, SD, median and range values will be used to  
231 summarize the continuous data. The primary outcome (number of steps per week) will be analyzed using  
232 multiple linear regressions. Particularly, we will test whether the participants' physical activity level  
233 (number of steps) the week after intervention termination will be higher in the intervention group relative  
234 to the control group, after adjustment for covariates (i.e., age, sex). Furthermore, we will test whether  
235 participants' automatic approach tendencies towards physical activity will be higher and participants'  
236 automatic approach tendencies towards sedentary behaviours will be lower in the intervention group  
237 compared to the control group.

238 *Secondary Analysis*

239 The continuous outcomes will be analyzed using linear mixed-effects models, which account for  
240 the nested structure of the data (i.e., multiple observations within a single participant), thereby providing  
241 accurate parameter estimates with acceptable type-I error rates [49]. To examine the effect of the  
242 intervention on the evolution of physical activity and sedentary behavior, models will include interaction  
243 terms between group (intervention group vs. comparison group) and number of days within or after (follow-  
244 up) the intervention. We will treat the continuous secondary outcomes in the similar way to the primary  
245 outcome. R software will be exploited for all analyses.

246 ***Data Monitoring***

247 The principal investigator will instruct all project team members to ensure that the study will be  
248 carried out according to the protocol. Research assistants will need to understand the protocol before  
249 starting the data collection. The ethics committee may visit the research sites for quality assurance. No  

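### The primary outcome definition covers six assessment weeks while the primary analysis tests one, and neither the .0294 threshold nor the stopping rule names the endpoint it applies to

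*Combined protocol and SAP*

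**What the plan says.** The document is a combined protocol and SAP. It describes the primary endpoint in several places.

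- **Abstract.** "The primary outcome will be the number of steps per week", with no time point.
- **Experimental protocol.** Outcomes are collected for one week before the first session, in the week after the last session, and at the follow-ups ("intervention, as well as 1, 3, 6, and 12 months post intervention").
- **Outcomes, Primary outcome.** What serves as the primary outcome is the "number of steps measured in the week pre- and post-intervention, as well as 1, 3, 6, and 12 months after the" intervention. No single week, and no summary across weeks, is picked out.
- **Data analyses, Primary analysis.** Steps per week go into a multiple linear regression. The contrast singled out is whether the "number of steps) the week after intervention termination will be higher in the intervention group relative" "to the control group, after adjustment for covariates (i.e., age, sex"). Pre-intervention steps are not among the listed covariates. The same paragraph adds two comparisons from the approach-avoidance task, which is listed as a secondary outcome: whether "automatic approach tendencies towards physical activity will be higher and" whether those towards sedentary behaviours will be lower.
- **Threshold and stopping rule, same section.** "Based on the Pocock boundary, the threshold for significant p-values will be .0294", with one interim look at 50% of the data and one final look. Data collection ends if "the effect is significant at the interim analysis, thereby indicating that the data provide support for the" hypothesis.
- **Data analyses, Secondary Analysis.** The course of physical activity during and after the intervention is modelled by a linear mixed model with a group-by-days interaction.

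**The concern.** A trial that stops early on a p-value needs one endpoint behind that p-value. Here the outcome section lists six weeks and the analysis section tests one. The pre-intervention week precedes the first session, so the intervention cannot affect it. The other five weeks could each be presented as the primary outcome by citing the outcome section. The stopping rule does not settle the matter, because it refers to an effect without saying on which variable or at which week.

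Two things are at stake. The first is type I error: the Pocock threshold is calibrated for a single endpoint examined twice. The second is the interim itself. Half of the post-intervention step data will exist long before half of the 12-month step data, so the 50% point cannot be located until the endpoint is fixed. If the post-intervention week triggers the stop, then ending data collection, as worded, could also cut off follow-up weeks that the outcome section calls primary.

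**Working it through.** **1. The passages side by side**

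| Element | Primary outcome section | Primary analysis section |
|---|---|---|
| Pre-intervention week | part of the primary outcome | no role; covariates are age and sex |
| Post-intervention week | part of the primary outcome | the step contrast tested |
| 1, 3, 6 and 12 months | part of the primary outcome | not tested here; trajectory under Secondary Analysis |
| Approach tendencies | not included | two comparisons in the same paragraph |
| Endpoint for .0294 and the stop | not stated | not stated |

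**2. The plan's own figure, for one endpoint**

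Inputs from the Primary analysis section: nominal p = .0294, looks at 50% and 100% of the data. Assumption: two-sided tests, since sidedness is not stated.

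- Critical value: c = Φ⁻¹(1 − .0294/2) = 2.178.
- Correlation of the two test statistics: √.5 = .707.
- Overall alpha = 1 − P(|Z₁| < c and |Z₂| < c) = .0500.

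The threshold reproduces: it gives 5% overall for exactly one endpoint.

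**3. What the open definition would allow**

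Suppose significance at any of the five post-randomisation weeks could be reported as the primary result. I simulated 1,000,000 null trials with five step-count statistics of equal pairwise correlation rho. Each was tested two-sided at c, with Z₂ = (Z₁ + Z′)/√2, where Z′ is the independent second half of the data.

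- Scenario A: all five weeks tested at both looks, each at information fraction .5 at the interim.
- Scenario B: only the post-intervention week tested at the interim, all five at the end. This allows for the later weeks maturing later.

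| rho (assumed) | A: five weeks, both looks | B: post week at interim, five at end |
|---|---|---|
| .9 | .104 | .080 |
| .8 | .13 | .096 |
| .5 | .186 | .131 |
| 0 | .226 | .157 |

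Exact checks at rho = 0:

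- A: 1 − (1 − .05)⁵ = .226.
- B: 1 − (1 − .05)(1 − .0294)⁴ = 1 − .95 × .8875 = .157.

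Both agree with the simulation.

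**The case against.** The strongest reply is that the Primary analysis section already names one step comparison, the post-intervention week between groups. The outcome section can then be read as naming the variable and repeating the collection schedule. The follow-up weeks are not left without a method either, since the secondary mixed model covers them. On this reading the two sections differ in precision more than in substance, and .0294 is valid.

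Much of this stands. A reader might infer from the six-week definition that the trial's type I error is 13% to 23%, or that its error control is already lost. The documents do not support that. Nowhere do they plan five visit-wise tests at .0294 or declare success if any one is significant. The upper end of the range also needs step counts from the same people to be uncorrelated between weeks, which is implausible. The figures further depend on equal correlations, on how much of each week's data is in hand at the interim, and on two-sided testing, although the stated hypothesis is directional.

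What does not stand is the claim that the endpoint is therefore fixed. The outcome section assigns primary status to all the weeks, not just a collection schedule. The analysis text introduces the post-intervention contrast as a particular case and does not say that it is the only confirmatory test. The stopping rule names no endpoint in a paragraph that also holds two approach-tendency comparisons. No other section resolves this: the Abstract gives no time point, and the Discussion expects benefit both during the intervention and at follow-up.

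**Conclusion.** The concern holds as a failure to fix the primary endpoint. The outcome and analysis sections disagree about which weeks are primary, the baseline week is listed as an outcome, and the threshold and early stop are attached to no named outcome or time point.

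The size is conditional. If the post-intervention contrast alone is confirmatory, overall two-sided alpha is .050 and nothing is lost. If a result at any of the five weeks could be called primary, the familywise error would be about .10 to .23 in scenario A and about .08 to .16 in scenario B, for correlations from .9 down to 0. The correlations, information fractions and sidedness are not in the documents. These figures measure the latitude that the wording leaves; they are not an error rate to which the plan commits.

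It should still be corrected before any data are examined by group, because both the only stated error control and the stopping decision depend on it.

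**What to change.** 1. **Primary outcome section:** name one primary endpoint. The simplest choice is steps in the week following the last session, which the Primary analysis section already tests. If the sponsor prefers another time point or a summary across weeks, naming it cures the defect equally, but the primary analysis must then be changed to match.
2. **Same section:** describe the pre-intervention week as baseline. List the 1, 3, 6 and 12-month step counts as secondary outcomes, analysed in the existing mixed model.
3. **Primary analysis section:** state that the .0294 threshold and the interim stop apply only to that endpoint and not to the approach-tendency tests, and define 50% of the data in terms of that endpoint.
4. **Separate improvement, not needed to fix the endpoint:** add pre-intervention weekly steps as a covariate in the primary regression. The data are already collected, and the expected gain is precision.

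Cost: wording and one covariate, with no new data, visits or participants. With the post-intervention week as the endpoint, results at 1 to 12 months can no longer be called the primary result.

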171 **1. Reflective and automatic processes underlying physical activity**

172 (a) *Explicit Affective Attitude Toward Physical Activity*: Explicit attitudes toward physical activity will  
173 be calculated as the mean of two items (Cronbach's alpha = 0.92) based on two bipolar semantic  
174 differential adjectives on a 7-point scale (unpleasant-pleasant; unenjoyable-enjoyable). The  
175 statement begins with "For me, to participate in regular physical activity is ..." [42].

176 (b) *Approach-avoidance task*: A contextual approach-avoidance task will be used to measure  
177 automatic approach and avoidance tendencies toward physical activity and sedentary behaviors  
178 [36]. Participants will be asked to move a manikin on the screen "toward" (approach condition)  
179 and "away" (avoidance condition) from images depicting physical activity and sedentary behaviors  
180 by pressing keys on a keyboard. Each trial will be started with a black fixation cross presented  
181 randomly for 250–750 ms in the center of the screen with a white background. Then, the manikin  
182 will be appeared in the upper or lower half of the screen. Concurrently, a stimulus depicting  
183 "movement and active lifestyle" (i.e., physical activity) or "rest and sedentary lifestyle" (i.e.,  
184 sedentary behavior) will be presented in the center of the screen. Participants quickly must move  
185 the human figure "toward" a stimulus (approach) depicting physical activity and "away" from a  
186 stimulus (avoidance) depicting sedentary behaviors, or vice versa. After seeing the manikin in its  
187 new position for 500 ms, the screen will be cleared. In case of an incorrect response, error feedback  
188 (i.e., a cross) will be appeared at the center of the screen.

189 **2. Physical Functioning**

190 (a) *Usual Level of Moderate-to-Vigorous Physical Activity*: The usual level of physical activity  
191 will be derived from the short form of the International Physical Activity Questionnaire  
192 (IPAQ-SF). The IPAQ-SF is a self-administered questionnaire that identifies the frequency  
193 and duration of moderate and vigorous physical activity, as well as sedentary time during the  
194 past 7 days to estimate usual practice of physical activity and sedentary behavior [46]. The  
195 usual level of moderate-to-vigorous physical activity (MVPA) in minutes per week will be  
196 used as a control variable in the analyses.

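### IPAQ MVPA is both a secondary outcome and a control variable with no time point or model named, and the primary model's covariate list (age, sex) leaves it out

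*Combined protocol and SAP*

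**What the plan says.** The protocol deals with this variable in three places.

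- **Secondary Outcomes, item 2(a).** MVPA in minutes per week, from the IPAQ-SF, is listed as an outcome under Physical Functioning. The questionnaire covers the "past 7 days to estimate usual practice of physical activity and sedentary behavior". The same item says the variable will be "used as a control variable in the analyses". It names neither a visit nor a model.
- **Experimental protocol.** Primary and secondary outcomes "will be collected for one week, the week before the first session, the week following the last session of the" "intervention, as well as 1, 3, 6, and 12 months post intervention". If the IPAQ follows this schedule, each participant has up to six MVPA values, one before training and five after it.
- **Data analyses.** The Primary analysis compares steps in the week after the intervention, intervention group relative "to the control group, after adjustment for covariates (i.e., age, sex"). The Secondary Analysis describes mixed models with a group-by-days interaction and names no covariates. It adds: "We will treat the continuous secondary outcomes in the similar way to the primary" outcome.

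**The concern.** Two things are unsettled.

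First, the covariate sets do not match. Item 2(a) puts MVPA into the analyses without restriction. The primary model's list is introduced by an i.e. and stops at age and sex. An analyst could follow either statement and claim to have followed the plan. That matters more than usual here, because a significant interim result ends data collection.

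Second, the time point is open. A value from before training is an ordinary baseline covariate. A value from after training is itself a possible response to the intervention. With a 7-day recall it may also cover much the same days as the step count it would be adjusting. Conditioning on it would no longer estimate the total effect of allocation, which is what the stated intention-to-treat principle calls for. The same question arises in the mixed models, where repeated MVPA values could be entered as a time-varying covariate, and where MVPA is itself one of the outcomes.

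**Working it through.** **Inputs from the protocol.** Planning effect .39 SD and 108 per condition (Sample size); 1:1 allocation (Allocation and blinding); significance threshold .0294 (Primary analysis).

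**Assumed inputs.** *m*, the shift the intervention causes in post-intervention MVPA, in SD: .1, .2 or .39. *r*, the within-arm correlation of MVPA with post-intervention steps: .2, .4 or .6. The documents give neither. Testing is taken as two-sided, which is also not stated, and power is for the final look alone.

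**The plan's own figure.** The protocol puts no number on this covariate; its only design figure is the sample size. With n = 2(z_α + z_β)²/d², d = .39, power .90 and alpha .05, n is 113 per arm one-sided or 139 two-sided. The stated 108 comes out one-sided at d = .40. I take 108 as given, since the difference does not affect this point.

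**Step 1: no activity covariate.** SE = √(2/108) = .136. With a critical value of 2.178 at two-sided .0294, power for .39 SD is 75%.

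**Step 2: pre-intervention MVPA as covariate.** Training cannot affect a value recorded before the first session, so randomisation makes its expected group difference zero. The expected adjusted effect stays .39, and SE = √(1 − r²) × .136:

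| r | SE | Power |
|---|---|---|
| .2 | .133 | 77% |
| .4 | .125 | 83% |
| .6 | .109 | 92% |

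**Step 3: post-intervention MVPA as covariate.** With both variables in within-arm SD units:

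- adjusted effect = .39 − r·m
- share removed = r·m/.39
- SE = √(1 − r²) × √[(2/108)(1 + m²/4)]

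| m | r | Adjusted effect | Share removed | Power |
|---|---|---|---|---|
| .1 | .2 | .370 | 5% | 72% |
| .1 | .4 | .350 | 10% | 73% |
| .1 | .6 | .330 | 15% | 80% |
| .2 | .2 | .350 | 10% | 67% |
| .2 | .4 | .310 | 21% | 62% |
| .2 | .6 | .270 | 31% | 61% |
| .39 | .2 | .312 | 20% | 55% |
| .39 | .4 | .234 | 40% | 37% |
| .39 | .6 | .156 | 60% | 22% |

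Worked row (m = .39, r = .4): .39 − .4 × .39 = .234, and .156/.39 = 40%.

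Power does not fall in every row. At m = .1 and r = .6 it is 80%, above the 75% of Step 1, because the smaller residual variance outweighs the attenuation. What every row shares is a coefficient that understates the total effect.

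**Check by simulation.** With 400,000 simulated participants, m = .39 and r = .5, the group coefficient was about .20 when adjusting for the post-intervention value and .394 when adjusting for the baseline component. The formulas give .195 and .39.

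**The case against.** The best defence is that a pre-intervention value is meant. The item speaks of a usual level and calls it a control variable, which is how one describes a baseline characteristic, and the Experimental protocol does schedule a measurement before the first session. On that reading there is no bias and some gain in precision. This stands as a plausible reading, but the text does not state it.

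A reader might go further the other way and infer that the plan does adjust for a post-randomisation measure, so that the step difference will be biased toward zero. The documents do not support that. Attenuation needs three things together: a post-intervention value in the model, an upward shift in self-reported MVPA caused by the intervention, and a positive within-arm correlation with steps. None is established. The overlap between the recall period and the tracker week is also uncertain, since the day on which the questionnaire is completed is not given. If it is completed early in that week, recall falls largely in the last training week. The upper rows of loss require MVPA to move by the full .39 SD, a figure the protocol gives only as the planning effect of go/no-go interventions.

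On the covariate conflict, one can argue that the age and sex list governs only the primary regression and that MVPA was meant for the mixed models. Item 2(a) makes no such restriction, and the Secondary Analysis names no covariates, so the mismatch remains.

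**Conclusion.** The specification gap and the conflict between the two sections are certain from the text, and nothing elsewhere in the protocol resolves them. Bias is a possibility that the plan fails to exclude; it is not something the plan prescribes. Expected loss is zero if the pre-intervention value is used. If a post-intervention or time-varying value were used, about 5% to 60% of a .39 SD effect could be adjusted away over the assumed ranges of m and r. The power figures rest on those same assumptions, on two-sided .0294 and on the final look only. The plan should be corrected before analysis, because one unstated choice decides whether this covariate helps or harms.

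**What to change.** 1. Write the same covariate list in Secondary Outcomes item 2(a) and in Data analyses: age, sex and one named pre-intervention activity measure, with a statement of which models use it.
2. For that measure, tracker steps from the pre-intervention week are preferable, being the baseline value of the primary outcome and already scheduled. Pre-intervention IPAQ MVPA would also cure the defect, so the choice between the two is a matter of efficiency.
3. State that MVPA measured after the first session is analysed only as an outcome and enters no model of the intervention effect as a covariate.

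The cost is a sentence or so in each of two sections, with no new data and no added participant burden. At the assumed correlations of .2, .4 or .6 between the baseline measure and post-intervention steps, power at 108 per arm would rise from 75% to about 77%, 83% or 92%.

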53 with fear, pain, or discomfort felt during physical exercise. Therefore, older adults could be particularly  
54 responsive to and benefit the most from an intervention targeting the automatic reactions to physical activity  
55 and sedentary stimuli.

56 Interventions targeting automatic reactions to health-related stimuli have already proven to be  
57 successful in changing behavior [26-32]. For example, interventions have been used to retrain the automatic  
58 reaction to alcohol [27]. Using a joystick, patients were repeatedly asked to avoid pictures on a screen that

59 were related to alcohol and to approach pictures unrelated to alcohol. Results showed that adding to a  
60 regular treatment an intervention targeting cognitive bias reduced the relapse rates one year after treatment  
61 discharge by 9% to 13% [27-29]. These interventions have also proven to be useful in impacting smoking  
62 [30], social anxiety [31], and eating behavior [32]. Based on these encouraging results, the current project  
63 proposes to test the effect of a cognitive-bias intervention on another health behavior: physical activity.

64 **Primary aim**

65 The overall primary objective of this project is to investigate the effectiveness of an intervention  
66 targeting automatic reactions to physical activity and sedentary stimuli in older adults.

67 **Secondary aim**

[figure not shown]
68 The secondary objective is to test the effects of the intervention on reflective and automatic  
69 processes underlying physical activity, physical functioning, and quality of life.

70

71 **Methods**

72 **Study design and settings**

73 Our study follows a placebo (sham-controlled), double-blinded design with a 12-month follow-up  
74 (Figure 1).

75

**Figure 1.** Study design

76

77 ***Participants***

78 Older adults aged 60 years and older will be enrolled in the study.

79 ***Recruitment***

80 Recruitment will occur by placing posters in a: strategic areas, such as public areas where permissible and  
81 b: posting on social media (Facebook, Twitter). Interested seniors will be asked to contact the researcher  
82 directly. Once the interested person initiates the contact leaving a phone message or sending an e-mail, we  
83 will follow up on them and will invite them to attend in an in-person meeting aiming to increase their  
84 intention to be physically active based on the “Ask-Assess-Advise” approach and to inform them about the  

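### As worded, a significant interim result ends data collection, which would cut the 1- to 12-month visits of enrolled participants; nothing limits the stop to enrolment

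*Combined protocol and SAP*

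**What the plan says.** The Primary analysis section plans a sequential analysis, "conducted with an interim analysis after 50% of the data is collected and the other analyses after all data is" collected, with a Pocock threshold of .0294. If the interim effect is significant, "data collection will be terminated". The step comparison named in that section is whether steps in "the week after intervention termination will be higher in the intervention group relative" to controls, by multiple linear regression adjusted for age and sex. The same section then adds tests of automatic approach tendencies.

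Other sections rely on long follow-up:

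- Study design and settings describes a "double-blinded design with a 12-month follow-up".
- Experimental protocol has primary and secondary outcomes collected before and after the intervention, "as well as 1, 3, 6, and 12 months post intervention".
- Primary outcome defines the outcome as the "number of steps measured in the week pre- and post-intervention, as well as 1, 3, 6, and 12 months after the" intervention.
- Secondary Analysis fits mixed models with a group-by-days interaction that covers the follow-up period.
- The Discussion expects a benefit at follow-up as well as during the intervention.

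**The concern.** The stopping sentence ends data collection, not recruitment. The sections on recruitment, sample size, data management and data monitoring do not narrow it. Where the plan uses the term elsewhere, it means gathering data: under Allocation and blinding, the research assistant guesses allocation at the "end of data collection phase".

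A result on the week after training could therefore end the collection of later visits that the plan counts in its primary outcome. The claim at stake is whether any gain in steps lasts. Skipped visits cannot be recovered afterwards.

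The amount lost depends on when the interim happens, and the plan does not define half of the data. It could mean half the participants with the post-intervention week, half with complete follow-up, or half of all assessments.

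**Working it through.** **1. The plan's threshold.** Two looks, at 50% and 100% of the information, have correlation √0.5. A two-sided .0294 at each look gives an overall alpha of .0500, so the figure reproduces as a two-sided boundary. Used one-sided, it gives .0485.

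**2. Chance of stopping at the interim.** Inputs: effect size .39 and 108 per arm (Sample size), 1:1 allocation (Allocation and blinding). Assumption: the interim is at 54 per arm.

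- Noncentrality = .39 × √(54/2) = 2.03.
- Critical value for two-sided .0294 = 2.18.
- Chance of crossing = .440 (normal) or .431 (noncentral t, 106 df).
- With noncentral t, a true effect of .30 gives .262 and one of .20 gives .126.

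**3. Visits cut if the sentence is followed literally.** Assumptions: 216 participants enrol uniformly over T months, with no dropout. Participant i enrols at iT/216 months. The baseline week, three training weeks and post week take 5/4.345 = 1.15 months. The visit at m months is complete m months after that.

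*Interim when participant 108 finishes the post week* (time T/2 + 1.15). Enrolled = 108 + 216 × 1.15/T. Visits done at month m = 108 − 216m/T, with a floor of 0.

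| T (months) | 6 | 12 | 24 | 36 |
|---|---|---|---|---|
| Enrolled | 149 | 128 | 118 | 114 |
| Follow-up visits due (× 4) | 596 | 512 | 472 | 456 |
| Done at 1/3/6/12 months | 72/0/0/0 | 90/54/0/0 | 99/81/54/0 | 102/90/72/36 |
| Cut | 524 (88%) | 368 (72%) | 238 (50%) | 156 (34%) |

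*Interim when participant 108 finishes the 12-month week* (time T/2 + 13.15). Visits done at month m = 108 + 216(12 − m)/T, capped at the number enrolled.

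| T (months) | 6 | 12 | 24 | 36 |
|---|---|---|---|---|
| Enrolled | 216 | 216 | 216 | 186 |
| Follow-up visits due (× 4) | 864 | 864 | 864 | 744 |
| With a 12-month visit | 108 | 108 | 108 | 108 |
| Cut | 108 (12.5%) | 108 (12.5%) | 198 (23%) | 156 (21%) |

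*Interim at half of the 216 × 6 = 1,296 assessments.* The share cut is 72/58/40/29%, with 216/183/150/136 enrolled and 0/0/32/57 participants having a 12-month visit.

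**4. Precision at 12 months.** The 95% half-width for the group difference, in SD units, is 1.96 × 2/√N.

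- Post-week trigger, literal stop: not estimable for T = 6, 12 and 24; .65 for T = 36 (N = 36).
- Post-week trigger, enrolment-only stop: .32 to .37 (N = 149 to 114).
- 12-month trigger: .38 under the literal stop (N = 108), against .27 to .29 if only enrolment stops (N = 216 or 186).

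**The case against.** A stopping rule normally overrides the schedule that applies if a trial continues, so the follow-up sections and the stopping sentence need not contradict each other. The sentence comes right after talk of half and then all of the data, so it can be read as not collecting the second half of the sample. On that reading nothing is lost. The blinding passage only dates a guess about allocation and does not define what the interim ends. Mixed models can also be fitted to incomplete follow-up, with less precision. All of this stands. It makes the sentence ambiguous rather than plainly wrong, but it does not supply the missing limit.

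The size is also open to challenge. Accrual is assumed. The effect of .39 comes from a meta-analysis of eating-behaviour interventions, so the crossing chance could be well below 43-44%. If half of the data means half the participants with complete follow-up, the loss is modest. These points stand too, and for that reason the result is given as a range.

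Stopping enrolment only does not always preserve the benefit of an early stop. In 4 of the 12 scenarios all 216 are already enrolled at the interim: the 12-month trigger at T = 6, 12 and 24, and the assessment trigger at T = 6. An enrolment-only stop then saves nothing. This is correct, and it is why the fix has to set the trigger as well.

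A reader might infer that no test is named for the interim. That goes too far: the same section names the regression on post-intervention-week steps. The remaining doubt is only that the approach-tendency tests share that section.

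**Conclusion.** The point holds as a wording defect with a real consequence if the sentence is followed literally; it should be fixed. Under the plan's own effect size an early crossing is quite likely (43-44% two-sided; 26% at .30 and 13% at .20, all at 54 per arm). Given a crossing, the literal rule cuts 34-88% of enrolled participants' follow-up visits with a post-week trigger and 12.5-23% with a 12-month trigger. Both ranges rest on uniform enrolment over 6 to 36 months and no dropout, which the plan does not state.

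Two stronger readings are tempting and not supported. The first is that the trial would end without 12-month data. That happens in 5 of the 12 scenarios, all with an early trigger and faster accrual, and not at all if the authors meant accrual only. The second is that the main result is compromised. The post-intervention-week comparison made at the interim is unaffected; what is lost is evidence on durability.

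**What to change.** Amend the Primary analysis section in three places.

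1. State that crossing the boundary stops enrolment only, and that every randomised participant completes all scheduled visits through 12 months.
2. Define the interim as half of the planned participants, 54 per arm, with the post-intervention-week step outcome. With a later trigger, all 216 may already be enrolled and an enrolment-only stop would save nothing.
3. State that the effect tested is the group difference in post-intervention-week steps from the primary regression, not the approach-tendency tests in the same section.

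The .0294 threshold and 108 per arm do not change. The cost is that visits already planned for enrolled participants are still carried out and paid for after an early positive result. The interim result should also be kept from participants and the research assistant while those visits continue, and the plan should say so.
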